7.6.2 Lapatinib/Placebo Modifications

Patients will be treated per protocol as described in Section 7.2.2 or until disease progression or withdrawal from treatment due to unacceptable adverse event or treatment consent withdrawal.

If lapatinib dose reduction is required the following general rules should be applied:

- Lapatinib/placebo dose should be reduced by increments of 250 mg at a time and only after all supportive care measures have been exhausted without an improvement of patient status.
- Lapatinib/placebo should not be used at doses below 1000 mg if given as monotherapy or below 750 mg concomitantly with cisplatin.

See the table below for a summary of dose holding/interruptions and dose de-escalation recommendations in case of lapatinib-related adverse events (graded according to CTCAE, v. 4). See Section 7.7 below for management guidelines of lapatinib adverse events.

Adverse Event (CTCAE, v. 4)	Action
Non-hematological, grade 1 or 2 (Not attributable to cisplatin or radiation)	Continue lapatinib therapy at full dose prescribed. Apply maximum supportive care recommendations. If prolonged duration of grade 2 adverse event is affecting quality of life a one-time decrease of dose by 250 mg is allowed.
Non-hematological, grade 3 or 4 (Not attributable to cisplatin or radiation)	
Apply maximum supportive care recommendations. Hold lapatinib therapy until recovery to grade ≤ 1 (up to 14 days).
 
In patients with symptomatic grade 3 or 4 left ventricular cardiac dysfunction, lapatinib must be permanently discontinued. For grade 3 or 4 interstitial pneumonitis or grade 4 rash manifested as toxic epidermal necrolysis (e.g. Stevens-Johnson Syndrome etc.), lapatinib must be permanently discontinued.
 
If recurrence of adverse event after drug hold and/or interruptions is observed and maximum supportive care measures applied, a dose reduction by 250 mg is recommended. Lapatinib should not be used at doses below 1000 mg if given as monotherapy or 750 mg in combination with chemoRT. NOTE: The 750 mg dose should only be used after all supportive measures have been exhausted.

Non-hematological, grade 3 or 4 and adverse events NOT resolved to grade ≤ 2 within a maximum of 14 calendar days from last planned administration	Dose reductions by 250 mg (up to 2 reductions) will be considered after maximum supportive care recommendations are introduced.

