Cardiac* *Severity corresponding to NYHA criteria; see Appendix II.	Lapatinib therapy to be discontinued permanently in the case of symptomatic NYHA class III and IV congestive heart failure OR decrease in LVEF by $> 20\%$ relative to baseline or less than the institution's lower limit of normal.

Abnormal Liver Function Tests	
In the event of grade 3 or 4 abnormal ALT and/or bilirubin, lapatinib must be discontinued permanently. Refer to Section 7.7.4.
 
For grade 1 or 2 abnormal ALT/bilirubin, lapatinib must be discontinued permanently for patients with:
 
 • BOTH bilirubin and ALT abnormalities being of grade 2 
OR
 
 • EITHER bilirubin OR ALT abnormality is grade 2 and accompanied by signs or symptoms which, in the opinion of the treating physician, are related to liver injury caused by lapatinib. 
Such signs and symptoms may include abdominal pain, fever, jaundice, rash, eosinophilia or a PS drop of ≥ 1 point from baseline. Refer to Section 7.7.4.

In case of multiple short interruptions of dose due to either adverse events or drug supply or other reasons the sum of days without lapatinib treatment should not exceed 21 days in any 90 day treatment period.
	

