7.7 Management of Lapatinib/Placebo Adverse Events (8/5/14)

NOTE: SEE APPENDIX V FOR MANAGEMENT OF DIARRHEA.

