7.7.4 Management of Hepatotoxicity

Liver chemistry stopping and follow up criteria have been designed to assure patient safety and evaluate liver event etiology. All patients who meet liver chemistry criteria requiring permanent discontinuation of investigational product must continue to be followed per the Liver Chemistry Follow-up Criteria below.

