7.7.4.2 Interruption Criteria

If a patient experiences:

- ALT $>8 \times \text{ULN}$ or
- ALT $>5 \times \text{ULN}$ persisting for > 14 calendar days: retest within 3 days from the first occurrence and then every 7 calendar days to determine if ALT elevation persists or
- ALT $>3 \times \text{ULN}$ with signs or symptoms of hepatitis or hypersensitivity (the appearance or worsening of fatigue, nausea, vomiting, right upper quadrant pain or tenderness, fever, rash, or eosinophilia)

then hold investigational product for 14 calendar days, repeat liver chemistry testing in 14 calendar days, and then contact the Principal Investigator, [name], to discuss the possibility of re-starting lapatinib. Liver chemistries and aforementioned signs and symptoms should be monitored at a minimum of every 14 calendar days until resolution, stabilization, or a return to baseline values, at which point monitoring should be continued per protocol.

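### For a marked isolated ALT rise that is lapatinib-related or unexplained, 7.6.2 requires a permanent stop while 7.7.4.2 allows a restart discussion, and no text says which governs

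*Combined protocol and SAP*

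**What the plan says.** **Section 7.6.2, liver row of the table.** "In the event of grade 3 or 4 abnormal ALT and/or bilirubin, lapatinib must be discontinued permanently". Because the row says and/or, a rise in ALT alone is covered. The row then refers to 7.7.4. The introduction to the table describes it as a summary of holding and dose-reduction advice "in case of lapatinib-related adverse events (graded according to CTCAE, v. 4"), and adds: "See Section 7.7 below for management guidelines of lapatinib adverse events". The rows for general non-hematological events exclude events attributable to cisplatin or radiation. The liver row carries no attribution wording of its own.

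**Section 7.7.4, introduction.** "Liver chemistry stopping and follow up criteria have been designed to assure patient safety and evaluate liver event etiology". It also says that patients who meet a permanent-stop criterion must continue under the liver follow-up criteria.

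**Section 7.7.4.2.** Three ALT triggers are listed: above 8 × ULN; above 5 × ULN for more than 14 days; and above 3 × ULN with signs or symptoms of hepatitis or hypersensitivity. For any of them the instruction is: "then hold investigational product for 14 calendar days, repeat liver chemistry testing in 14 calendar days, and then contact the Principal Investigator", with the stated purpose "to discuss the possibility of re-starting lapatinib".

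**The concern.** A site that sees a high isolated ALT reads in one section that the drug is finished for that patient. In the section it is sent to next, it reads that the drug is paused and may come back. Both sections stop the drug at once, so the conflict concerns what happens after the 14-day retest.

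The stake is whether a patient with a marked ALT rise is re-exposed to a drug for which 7.4.6.2 acknowledges hepatobiliary events. The Principal Investigator, who decides, has no written rule on whether restart is open after grade 3 or 4 ALT. Any restart agreed for a lapatinib-related event would breach 7.6.2 as it stands.

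**Working it through.** **Step 1. Which rule covers which ALT.**

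| Section | ALT condition | Other condition | Action |
|---|---|---|---|
| 7.6.2 liver row | grade 3 or 4 | none in the row; table covers lapatinib-related events | permanent stop |
| 7.7.4.1 | > 3 × ULN | total bilirubin > 2.0 × ULN as well | permanent stop, no re-challenge |
| 7.7.4.2 | > 8; or > 5 for > 14 days; or > 3 with symptoms (× ULN) | none on bilirubin or cause | 14-day hold, retest, restart discussion |
| 7.7.4.3 | > 3 and < 5 × ULN | bilirubin ≤ 2 × ULN, no symptoms, weekly monitoring possible | continue; stop if it lasts > 28 days |

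For an isolated ALT above 8 × ULN, 7.7.4.1 does not apply because its bilirubin condition is not met, and 7.7.4.3 does not apply because ALT is too high. That leaves 7.6.2 and 7.7.4.2.

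**Step 2. Whether the overlap depends on the grade 3 cut-off.** The documents do not print the CTCAE cut-off, so call it g × ULN. The first trigger in 7.7.4.2 has no ceiling, so both rules apply to every isolated ALT above max(8, g) × ULN:

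- g = 3, 5 or 8: overlap starts at 8 × ULN
- g = 10: overlap starts at 10 × ULN
- g = 20: overlap starts at 20 × ULN

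The overlap is not empty for any g.

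**Step 3. Whether anything else resolves it.** No sentence in 7.4.6.2, 7.6.2 or 7.7.4 ranks the rules. The cap in 7.6.2 of 21 days without drug in any 90 does not block a restart, since the hold is 14 days. The section dates do not rank them either: 7.6 is dated 3/22/16 and 7.7 is dated 8/5/14.

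**Step 4. Exposure range for one patient.** Inputs: 7 lead-in days and 42 days with radiotherapy (7.2.2); maintenance of 3 months, taken as 91 days; and the liver test due 4 weeks after drug start (11.2.5), taken as day 28.

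- Planned drug: 7 + 42 + 91 = 140 days.
- Permanent stop at day 28: 28/140 = 20%.
- Hold of 14 days, immediate restart, no later interruption: (140 − 14)/140 = 126/140 = 90%.
- Difference: 126 − 28 = 98 daily doses, or 0 if restart is refused.
- With maintenance taken as 84 days: 28/133 = 21%, 119/133 = 89%, difference 91 doses.

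**The case against.** The strongest defence is attribution. The 7.6.2 table is about lapatinib-related events, while 7.7.4 exists partly to find the cause: 7.7.4.4 asks for viral serology, CPK, LDH and a record of other hepatotoxins. On that reading the hold and work-up come first. A lapatinib-related event then meets the 7.6.2 stop, and an event with another cause goes to a restart discussion. This is coherent, and it stands to the extent that one should not claim a conflict where another cause is established. But the sequence is not written. 7.7.4.2 sets no attribution condition on restart, so the conflict remains for lapatinib-related events. It is also unsettled for unexplained ones, which matters in a double-blind trial where the investigator judges attribution without knowing the assignment.

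A second defence is that a site can satisfy both sections by holding, retesting, calling and not restarting. That is true, but 7.7.4.2 expressly opens a restart that 7.6.2 forbids. A third is that a summary table yields to the section it cites. No text says so, the row is mandatory, and the reference to 7.7.4 can equally mean its follow-up work-up.

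Some stronger readings are tempting, and the documents do not support them:

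- **Sites will diverge freely.** Restart goes through a single central decision-maker.
- **98 doses is the effect.** It is the top of a range that includes zero.
- **Restarted patients go unmonitored until 3 months after radiotherapy.** The routine test schedule is a separate matter, and 7.7.4.2 requires checks at least every 14 days until values settle.
- **Compliance scoring under 7.8 breaks down because of this conflict.** 7.8 prints no event-level scoring rule for anything, so the gap is not specific to this point.

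**Conclusion.** The inconsistency is real and should be corrected. For an isolated ALT above both 8 × ULN and the grade 3 cut-off, where the event is lapatinib-related or has no established cause, 7.6.2 and 7.7.4.2 give incompatible answers on restart and no text ranks them. This conclusion needs no outside figure, because it holds for any grade 3 cut-off.

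The size is limited. The number of patients affected cannot be estimated, since the documents give no event rate and none is assumed. The exposure range of 0 to 98 daily doses (0 to 91 with 84 days of maintenance) rests on three assumptions: detection on day 28, restart on the day of the retest, and no later interruption.

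A reader might infer that the primary analysis is compromised. It is not: the analysis set (all randomized patients), the 69-event target and the 0.1803 significance level do not depend on which liver rule is followed.

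**What to change.** Add one sentence to 7.7.4.2:

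> Restart may not be considered if a permanent-discontinuation condition in Section 7.6.2 or 7.7.4.1 is met; grade 3 or 4 ALT that is lapatinib-related, or for which no other cause is established, is a permanent stop with no re-challenge.

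Keep all three 7.7.4.2 triggers as grounds for the immediate hold and work-up. No deletion is then needed, so the edit does not depend on the unprinted grade 3 cut-off. Restart stays available, through the Principal Investigator, where the work-up establishes another cause and no permanent-stop condition is met.

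The cost is the added sentence and a memo to sites, with no new tests or data. The downside is that some patients with an unexplained or lapatinib-related grade 3 or 4 ALT lose the chance of a centrally approved restart. In the week-4 case that is up to 14 of the 20 planned weeks of drug.

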7.7 Management of Lapatinib/Placebo Adverse Events (8/5/14)

NOTE: SEE APPENDIX V FOR MANAGEMENT OF DIARRHEA.

7.7.1 Management of Non-Hematologic Adverse Events

If any of the following conditions occur, administration of lapatinib/placebo may be interrupted for a maximum of 14 days to allow the adverse event (AE) to resolve or decrease in severity:

- CTCAE, v. 4 grade 3 or 4 or unacceptable adverse events, e.g. cosmetic effect of grade 2 rash;
- No consideration and/or corroborative evidence that the AE is due to progressive disease;
- The AE is consistent with previously described lapatinib/placebo AEs. At a minimum, reassessment of AEs should be done weekly and more frequently if clinically indicated. When the AE decreases in severity to CTCAE, v. 4 grade 1, the patient may continue to take the assigned dose.

7.7.2 Management of Asymptomatic Cardiac Adverse Events

Refer to CTCAE v. 4 grading of left ventricular cardiac function. After the baseline ECHO or MUGA, repeat LVEF assessment is required at week 12. If a patient is found to have a $\geq 20\%$ decrease in LVEF relative to baseline, or the ejection fraction is below the institution's lower limit of normal, then lapatinib/placebo should be permanently discontinued, and the patient should have a repeat evaluation of ejection fraction 28 calendar days later to confirm recovery.

7.7.3 Management of Symptomatic Cardiac Adverse Events

Study medication must be withdrawn if a patient develops symptoms of heart failure or test results indicating abnormal LVEF (see Section 7.7.2).

7.7.4 Management of Hepatotoxicity

Liver chemistry stopping and follow up criteria have been designed to assure patient safety and evaluate liver event etiology. All patients who meet liver chemistry criteria requiring permanent discontinuation of investigational product must continue to be followed per the Liver Chemistry Follow-up Criteria below.

7.7.4.1 Permanent Discontinuation Criteria

If a patient experiences ALT $> 3 \times$ ULN and total bilirubin $> 2.0 \times$ ULN ($> 35\%$ direct; bilirubin fractionation required), then the following actions must be taken:

- Immediately and permanently discontinue investigational product;
- In addition to the liver event follow up assessments, the following are suggested: specialist or hepatology consultation; anti-nuclear antibody, anti-smooth muscle antibody, and Type 1 anti-liver kidney microsomal antibodies; and liver imaging and/or liver biopsy to evaluate liver disease;
- Promptly report the event to Novartis within 24 hours of learning its occurrence;

- Monitor every 7 calendar days until liver chemistries resolve, stabilize or return to within baseline values;
- Do not re-challenge with investigational product.

NOTE: If bilirubin fractionation testing is unavailable and a patient meets the criterion of total bilirubin $>2.0 \times \text{ULN}$, then the management of hepatotoxicity actions above must still be performed.

7.7.4.2 Interruption Criteria

If a patient experiences:

- ALT $>8 \times \text{ULN}$ or
- ALT $>5 \times \text{ULN}$ persisting for > 14 calendar days: retest within 3 days from the first occurrence and then every 7 calendar days to determine if ALT elevation persists or
- ALT $>3 \times \text{ULN}$ with signs or symptoms of hepatitis or hypersensitivity (the appearance or worsening of fatigue, nausea, vomiting, right upper quadrant pain or tenderness, fever, rash, or eosinophilia)

then hold investigational product for 14 calendar days, repeat liver chemistry testing in 14 calendar days, and then contact the Principal Investigator, [name], to discuss the possibility of re-starting lapatinib. Liver chemistries and aforementioned signs and symptoms should be monitored at a minimum of every 14 calendar days until resolution, stabilization, or a return to baseline values, at which point monitoring should be continued per protocol.

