7.7.4.3 Continuation Criteria

If a patient experiences ALT $>3 \times \text{ULN}$ but $<5 \times \text{ULN}$ and total bilirubin $\leq 2 \times \text{ULN}$, without signs or symptoms of hepatitis or hypersensitivity, and who can be monitored every 7 calendar days, then the following actions should be taken:

- Continue investigational product;
- Monitor every 7 calendar days until liver chemistries resolve, stabilize, or return to within baseline, then monitor liver chemistries as per protocol assessment schedule;
- If ALT >3 and $< 5 \times \text{ULN}$ persists for > 28 calendar days, discontinue treatment

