7.7.4.4 Liver Chemistry Follow-up Criteria

For all patients who meet any of the liver chemistry criteria described above, make every attempt to carry out the liver event follow up assessments described below:

Viral hepatitis serology including:

- Hepatitis A IgM antibody;
- Hepatitis B surface antigen and Hepatitis B Core Antibody (IgM);
- Hepatitis C RNA;
- Cytomegalovirus IgM antibody;
- Epstein-Barr viral capsid antigen IgM antibody (or if unavailable, obtain heterophile antibody or monospot testing);
- Hepatitis E IgM antibody (if patient resides or has traveled outside USA or Canada in past 3 months).

Serum creatine phosphokinase (CPK) and lactate dehydrogenase (LDH):

- Complete blood count with differential to assess eosinophilia;
- Record the appearance or worsening of clinical symptoms of hepatitis, or hypersensitivity, fatigue, decreased appetite, nausea, vomiting, abdominal pain, jaundice, fever, or rash as relevant on an AE report form;
- Record use of concomitant medications, acetaminophen, herbal remedies, other over-the-counter medications, other putative hepatotoxins, and/or alcohol use.

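### Two low-cost hepatic safety clarifications: weekly liver chemistry for patients whose drug is held, and a 24-hour report to RTOG for the ALT-plus-bilirubin event

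*Combined protocol and SAP*

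**What the plan says.** **Retest interval.** Section 7.7.4.2 covers three groups: ALT >8 x ULN, ALT >5 x ULN lasting more than 14 days, and ALT >3 x ULN with hepatitis or hypersensitivity symptoms. For all three the instruction is "then hold investigational product for 14 calendar days, repeat liver chemistry testing in 14 calendar days", followed by "Liver chemistries and aforementioned signs and symptoms should be monitored at a minimum of every 14 calendar days until resolution". For the >5 x ULN group, before the hold criterion is met, the same section asks sites to "retest within 3 days from the first occurrence and then every 7 calendar days to determine if ALT elevation persists".

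The neighbouring tiers differ. Section 7.7.4.1 (ALT >3 x ULN with total bilirubin >2.0 x ULN, drug stopped for good) says "Monitor every 7 calendar days until liver chemistries resolve, stabilize or return to within baseline values". Section 7.7.4.3 (ALT between 3 and 5 x ULN, no symptoms, bilirubin not above 2 x ULN, drug continued) says "Monitor every 7 calendar days until liver chemistries resolve, stabilize, or return to within baseline".

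The 7.6.2 table stops lapatinib permanently for grade 3 or 4 ALT and/or bilirubin and refers to 7.7.4. The opening of 7.7.4 says that patients who meet the permanent-stop criteria "must continue to be followed per the Liver Chemistry Follow-up Criteria below". Section 7.7.4.4 lists serology, CPK/LDH, a blood count and records of symptoms and medications. It gives no ALT or bilirubin retest interval.

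**Reporting.** For the ALT-plus-bilirubin event, 7.7.4.1 requires notice to the company within 24 hours and does not name the reporter. Section 7.9.2.1 makes the event an SAE. Sections 7.10 and 7.10.1 have sites report SAEs to RTOG, which holds the IND and informs FDA and the company. The 7.10.1 table sets 24 hours plus 5 calendar days for grades 4 and 5, and 10 calendar days below that. One cell requires no report for the lowest grade or grades without hospitalization; the table layout is unclear on how far that cell reaches.

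**The concern.** The middle tier has the longest required test interval. Being off drug does not fully explain this, because patients in 7.7.4.1 are off drug too and are tested weekly. A patient with ALT >5 x ULN is tested weekly until the hold begins, and the required interval then doubles.

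What is at stake is when a worsening is found. A held patient whose bilirubin passes 2.0 x ULN meets the permanent-stop and SAE definitions. The SAE report and the suggested hepatology consultation, autoantibody tests and imaging all wait for that result. The day-14 panel also informs the discussion about restarting, and it may be the only value from the hold.

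On reporting, one event carries two clocks. A site can follow the 7.10.1 table exactly and still miss the limit in 7.7.4.1, or meet that limit and leave the IND holder uninformed for days.

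**Working it through.** The plan states no figure to reproduce. The check compares the texts and does simple day counts.

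**1. Required liver-chemistry interval**

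| Section | Situation | Drug | Interval |
|---|---|---|---|
| 7.7.4.1 | ALT plus bilirubin | stopped | 7 days |
| 7.7.4.2, before the hold | ALT >5 x ULN, checking persistence | not yet held | within 3 days, then 7 days |
| 7.7.4.2, hold | three hold criteria | held | 14 days |
| 7.7.4.3 | ALT 3 to 5 x ULN, no symptoms | continued | 7 days |
| 7.6.2 table | stopped for ALT alone | stopped | none stated |

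**2. Does another schedule fill the gap?** Section 11.2.5 requires one bilirubin and AST/ALT test, 4 weeks after drug start. Appendix I next lists them 3 months after radiotherapy. Section 7.7.4.4 sets no interval. Section 7.7.1 asks for weekly reassessment of adverse events but names no liver test. None sets a shorter liver-chemistry interval.

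**3. Delay in detection.** Maximum: 14 − 7 = 7 days. Assume the bilirubin rise is equally likely on any day of the hold. Rises in the first week would then be found at day 7 instead of day 14 (gain 7 days), and rises in the second week at day 14 either way (gain 0). Mean gain: 0.5 × 7 + 0.5 × 0 = 3.5 days.

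**4. Extra tests.** Per two weeks: 14/7 = 2 panels against 14/14 = 1, so one extra per affected patient.

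**5. Reporting, non-grade-4/5 event on the 10-day clock**
- Through RTOG: site to RTOG by day 10, plus 1 day for RTOG's relay, is day 11. Against the 24-hour limit: 11 − 1 = 10 days late.
- Direct to the company on day 1, RTOG on the table's clock: 10 − 1 = 9 days between the company and the IND holder.

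The 7.6.2 table has a rule for ALT and bilirubin both at grade 2, so the protocol foresees combined events below grade 4. The CTCAE liver cut-points are not printed in the documents, so such events cannot be matched exactly to the ALT-plus-bilirubin definition.

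**6. Patients affected.** The rates are assumptions.
- Held or stopped for ALT, 1–5%: 71 × 0.01 = 0.7 to 71 × 0.05 = 3.6 in the lapatinib arm (142/2 = 71). If both arms had that rate: 142 × 0.01 = 1.4 to 142 × 0.05 = 7.1.
- ALT plus bilirubin, 0.5–2%: 71 × 0.005 = 0.4 to 71 × 0.02 = 1.4 in the lapatinib arm. If both arms: 142 × 0.005 = 0.7 to 142 × 0.02 = 2.8.

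**The case against.** The tiers have a rationale. Section 7.7.4.3 patients stay on drug, and being able to attend weekly is a condition of doing so. Section 7.7.4.1 patients also have raised bilirubin. Held patients are off drug without having met the bilirubin criterion, and 14 days is a floor. This explains part of the pattern. It does not explain why testing slows once the >5 x ULN patient gets worse, or why that patient may wait twice as long for the bilirubin result that would move them into 7.7.4.1.

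Section 7.7.1 says "At a minimum, reassessment of AEs should be done weekly and more frequently if clinically indicated", and the adverse event definition in 7.9.1 includes abnormal laboratory findings. A careful site could infer weekly ALT. But 7.7.4.2 is the specific rule and states 14 days, so the inference is not secure.

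The 7.6.2 table may move many held patients to a permanent stop. That would shrink the held group, but patients stopped for ALT alone have no stated interval either.

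Both reporting clocks can be met if the site notifies the company directly and files with RTOG by day 10. The 7.10.1 table also opens by asking for immediate reports to the sponsor. That is fair, but the immediate duty is then tied to the table's timeframes, and the IND holder can still be last to know.

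A reader might infer that sicker patients receive less safety care overall. The documents do not support that. The drug is stopped, the 7.7.4.4 work-up applies "For all patients who meet any of the liver chemistry criteria described above", and one hold group is defined by symptoms rather than by a higher ALT. Nor do they support a claim of longer drug exposure or of any effect on PFS or another endpoint.

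**Conclusion.** Both inconsistencies are present in the current text, and both are minor. The first can delay detection of a bilirubin rise in a held patient by at most 7 days, or 3.5 days on average under the uniform-timing assumption. The second can make the company report up to 10 days late, or leave the IND holder up to 9 days behind the company, when a site uses the full 10 days.

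It would go too far to call the two clocks irreconcilable, because direct notice to the company satisfies both. The number of patients affected cannot be taken from the documents; the assumed rates give only a handful. Section 13.5 expected accrual to finish around March 2017, so few patients may remain on treatment to benefit. The case for acting rests on the low cost of the changes and on the protocol's own recognition of hepatobiliary events with lapatinib.

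**What to change.** **1. Retest interval.** In 7.7.4.2, require liver chemistry every 7 calendar days during the hold and until values resolve, stabilize or return to baseline. State the same interval for patients stopped for ALT alone under the 7.6.2 table.

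Cost: one extra liver panel per affected patient per two weeks. The trial is double-blind, so this applies to both arms (142 patients in total). During radiotherapy the panel can share the weekly blood count and creatinine draw in Appendix I. In maintenance it needs an extra draw.

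**2. Reporting.** Add one line to the 7.10.1 table: the hepatic SAE defined in 7.9.2.1 (ALT >3 x ULN with total bilirubin >2.0 x ULN) needs an initial report to RTOG within 24 hours, whatever the CTCAE grade or hospitalization status, and a complete report within 5 calendar days of that. Leave the 24-hour company notice in 7.7.4.1 as it is.

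Cost: a 24-hour site clock for a very small number of patients in either arm. Neither change touches an endpoint, the sample size or an analysis.
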